Appendix B.	

STELLATE GANGLION BLOCKAGE IN COVID-19 POSITIVE PATIENTS
IRB#523-20-FB

Principal Investigator:

[name].
Assistant Professor
Director of Pain Clinics
Pain Medicine/Anesthesiology
University of Nebraska Medical Center

Supported by:

Department of Anesthesiology
University of Nebraska Medical Center

UNMC Nebraska Neuroscience Alliance COVID-19 Rapid Response Grants

NCT Number:

04445337

Brief Summary:

The proposed research plan will reflect the proof of concept of our modified stellate ganglion block in the human subject, following several key cardiac and pulmonary parameters leading to clinical benefit as well as the safety aspects of stellate ganglion blockade (SGB). Enrolling subjects will be enrolled from patients cared for in the COVID ICU/progressive care at Nebraska Medicine.

Patient eligibility will be determined based on the following criteria; Any patient between the ages of 40-75 with laboratory established COVID-19 infection (via rRT-PCR) requiring critical care in an intensive care unit, signs or symptoms consistent with ARDS, at least 2 of the following (respiratory rate ≥ 30 breaths per min, oxygen saturation at rest $\leq 93\%$, $\text{PaO}_2/\text{FIO}_2 \leq 200$ mm Hg, bilateral infiltrates on chest radiograph or CT not due to cardiac failure, requiring non-invasive or invasive mechanical ventilation.) Block randomization will be used to determine equal allocation to control (labs, nitric oxide levels +SOC) and intervention group (labs, nitric oxide levels, SGB procedure, perineural catheter 5 days). Once enrollment criteria are met, baseline assessments will be completed by the Acute Pain Service (APS). They will place SGB and manage intervention group for 5 days. Data collection will be collected through Day 5 of hospital stay, discharge information will be documented, and survival at 90 days via telephone to complete SF 36 questionnaire.

Section 1.0 Objectives:

To assess the safety, tolerance, oxygenation, lung and cardiac function, proinflammatory immune response and nitric oxide changes associated with the use of our modified SGB protocol in patients with ARDS due to COVID-19 disease.

Secondary (to be confirmed at later trial phase): To determine the association of use of our modified SGB protocol in patients with ARDS due to COVID-19 disease on: incidence of cardiac arrhythmias associated with ARDS, need and duration of use of mechanical ventilation and extracorporeal membrane oxygenation (ECMO).

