If a woman of childbearing age is enrolled as a subject and there has not been a pregnancy test during their current inpatient stay, a urine or blood pregnancy test will be performed. Pregnancy will not be allowed for this study as the drug is absorbed systemically and there are known risks to the fetus.

Section 4.0 Registration Procedure:

A prospective block randomized phase I/II two arm unblinded trial of a modified SGB protocol incorporated into Standard of Care vs UNMC standard of care Only for ARDS COVID-19 patients.

Subjects and/or Legally Authorize Representative (LAR) will be approached while subject is in the ICU/progressive care. If subject is unable to participate in the consenting process, the LAR will be contact via telephone and/or video chat. Consents will be sent to LAR electronically. PI and/or Sub-I will be present for all consenting process regardless is the ICF process takes place in person or video digital presence.

The randomization will be done by using *Stratified Permuted Block Randomization* in which sequential trial participants will be subdivided into the strata as indicated by their age-groups ie; 40-59, 60-74, 75-85 years and thereafter allocated to study group via block randomization within the strata so that the balance between age groups between the two study groups stays close to equal throughout the trial.

Section 5.0 Treatment Plan of Research Design:

A prospective block randomized phase I/II two arm unblinded trial of a modified SGB protocol incorporated into Standard of Care vs UNMC standard of care Only for ARDS COVID-19 patients.

Sixteen subjects will be enrolled. Eight in the control arm and eight in the intervention SGB arm.

Subjects will be identified on the COVID unit. The study will be explained to the subject and if the subject wishes to voluntarily participate, the ICF will be signed. If the subject is unable to sign consent, the LAR consent will be utilized. If LAR is not present, an electronic link to the consent will be sent to the LAR via email.

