- b) Differences in mean/median values for SGB vs SOC will be assessed at treatment day 5 - adjusted for baseline levels
- c) Differences in changes from baseline levels for SGB vs SOC as measured by comparison in slope trends;
- d) Differences in frequency of adverse events for SGB vs SOC over the study period from treatment through 90 day of follow up;

Secondarily,

- e) Differences between SGB vs SOC in *frequency and time to occurrence of cardiac arrhythmias*;
- f) Differences between SGB vs SOC in frequency of *need for and duration of use mechanical ventilation and/or extracorporeal membrane oxygenation (ECMO)*;
- g) Differences between SGB vs SOC in survival experience over treatment period through 90 -day discharge follow up

Sample Size issues:

For power computations we assume that SGB will particularly have an impact in reduction of inflammatory response as measured by IL-6. Looking at a meta-analyses of IL-6 values [Ulhaq ZS, Soraya GV. Interleukin-6 as a potential biomarker of COVID-19 progression. *Med Mal Infect.* 2020;50:382–383. doi: 10.1016/j.medmal.2020.04.002. 2020/04/08] and picking the largest of studies of COVID patients [Qin C, Zhou L, Hu Z, Zhang S, Yang S, Tao Y, et al. Dysregulation of immune response in patients with COVID-19 in Wuhan, China. *Clin Infect Dis* 2020, <http://dx.doi.org/10.1093/cid/ciaa248> [pii: ciaa248].], we estimate the overall mean (SD) IL-6 for COVID-19 patients to be 21 pg/mL (30.1). Using these estimates we see that a sample of 16 patients equally randomized into SGB (n=8) and SoC (n=8) would provide sufficient power to observe magnitude of differences in mean of IL-6 from as small as about 50 pg/mL and larger with 80% power at the 5% significance level assuming 2-sided hypothesis testing. (see Power Figure). The study [Liu MH, Tian J, Su YP, Wang T, Xiang Q, Wen L. Cervical sympathetic block regulates early systemic inflammatory response in severe trauma patients. *Med Sci Monitor.* 2013;19:194–201.], indicates that SGB is capable of eliciting reductions of IL-6 between groups and from baseline of magnitudes of greater than 100 pg/mL within 72hrs of first injection.

Section 7.0 Study Parameters:

Baseline Assessments

- Current Fio₂/PaO₂ ratio
- Current type of ventilation and oxygen use
- Current production of nitric oxide via Niox
- Current blood pressure and heart rate parameters
- Labs: IL-1beta, TNF-alpha, IL-6, ABG, CRP
- Chest x-ray
- Need for mechanical ventilation or other support

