Statistical considerations for primary objective, the analysis would include means/medians (standard errors, IQRs) at each time point - and also represented by error bars - and comparisons using t test or the Mann-Whitney U test as appropriate. Multivariate analyses using Generalized estimating equations (GEE) and to compare longitudinal changes in the two groups adjusting for confounders and as well as ANCOVA based regression to measure before and after changes. Kaplan-Meier survival methods to measure time to defined thresholds and Cox regression to assess any impact of confounders.

For safety - AE's will be assessed by providing descriptive statistics related to their frequency (summarized by occurrence, percentage of occurrence, severity, seriousness, outcome, relation to treatment, start time summary, duration of AE analysis) as well as graphically via box plots and cumulative incidence plots indicative of distributions in the two trial groups. Non-parametric methods (e.g. Fisher Exact testing) will be used to statistically compare the period frequency of events between the two groups. In general, timely analysis, by creating summaries of adverse events and other safety measurements such as relevant vital signs, ECG, Laboratory abnormal findings will be done to keep a check on the increase in intensity of observations taken at baseline and/or new findings arisen after baseline.

Secondary measures:

Occurrence of cardiac arrhythmias, need for mechanical ventilation and/or ECMO as well as overall survival will be compared using time-to-event based methods (e.g. Kaplan-meier curves). The expectation is that any non-statistically significant but implied trends will be evaluated in larger phase IIb /III trial that will follow.

Stopping Rules:

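### Safety is the first-listed objective, but the only named between-arm adverse-event analysis beyond description is a low-powered test at 8 versus 8, with no confidence interval

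*Combined protocol and SAP*

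**What the plan says.** Section 1.0 opens the objectives with safety: "To assess the safety, tolerance, oxygenation, lung and cardiac function". Section 5.0 fixes the size: "Sixteen subjects will be enrolled. Eight in the control arm and eight in the intervention SGB arm". Section 6.0(d) lists the safety measure as "Differences in frequency of adverse events for SGB vs SOC over the study period from treatment through 90 day of follow up".

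Section 10.0 summarises adverse events descriptively (occurrence, percentage, severity, seriousness, outcome, relation to treatment, timing, duration) with plots by group. It then adds one formal comparison: "Non-parametric methods (e.g. Fisher Exact testing) will be used to statistically compare the period frequency of events between the two groups". Fisher's test is given as an example. No alpha, sidedness, power, effect measure or confidence interval is stated for it.

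The only two-sided 5% statement is in the sample-size text of Section 6.0, which concerns IL-6: "with 80% power at the 5% significance level assuming 2-sided hypothesis testing". Section 6.0(a) plans the size of the difference and its 95% interval for the continuous biomarkers; item (d) has no counterpart.

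Separately, the Stopping Rules in Section 10.0 test the SAE/ADR rate against a 10% background rate by exact binomial methods, for consideration by the DSMB.

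**The concern.** A trial of 16 patients sized on IL-6 cannot be expected to test adverse events with useful power. What it can do is show how large an excess of harm remains compatible with the data. The plan promises that information for the cytokines and omits it for the first-listed objective, where the only inferential output would be a p value.

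Fisher's test is also conservative at this size, so for a harm comparison it gives up some of the little power available. In addition, a frequency of events may be a count of patients or a count of events. Fisher's test needs one independent outcome per patient, and repeated events in one critically ill patient would break that condition.

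At stake is the safety evidence that a later trial would inherit: a bare p value, without the range of harm that eight treated patients leave open.

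**Working it through.** **Inputs.** Eight per arm (Section 5.0). Two-sided 5% is an assumption, borrowed from the IL-6 calculation in Section 6.0. The 10% control-arm risk is also an assumption: Section 10.0 gives 10% as the background SAE/ADR rate for the intervention's known risk, and the documents give no other adverse-event rate.

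**The plan's own safety figures.** The only ones are in the stopping table, and they reproduce. For 2 of 5: 1 − 0.9^5 − 5 × 0.1 × 0.9^4 = 1 − 0.59049 − 0.32805 = 0.0815, as stated. The other three rows give 0.0702, 0.0556 and 0.0432, and the four lower limits also match. No figure is stated for the between-arm test.

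**Fisher p values, two-sided.**
- 4/8 v 0/8: 2 × C(8,4)/C(16,4) = 2 × 70/1820 = 0.077, not significant.
- 5/8 v 0/8: 2 × C(8,5)/C(16,5) = 2 × 56/4368 = 0.026, significant.
- 6/8 v 1/8 and 7/8 v 2/8: 0.041 each, significant.

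One-sided, 4/8 v 0/8 gives 70/1820 = 0.0385.

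**Power for 50% v 10%.** Sum P(control count) × P(SGB count significant), using Binomial(8, 0.1) and Binomial(8, 0.5):
- control 0, SGB 5 or more: 0.4305 × 0.3633 = 0.1564
- control 1, SGB 6 or more: 0.3826 × 0.1445 = 0.0553
- control 2, SGB 7 or more: 0.1488 × 0.0352 = 0.0052
- control 3, SGB 8: 0.0331 × 0.0039 = 0.0001

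The total is 0.217; rejections in the wrong direction add almost nothing.

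**Boschloo's test on the same 81 tables.** Its p value for 4/8 v 0/8 is 0.028. It rejects every table that Fisher's test rejects, plus 4 v 0, 8 v 4 and their mirror images. At 50% v 10% the 4 v 0 table adds 0.2734 × 0.4305 = 0.1177, and 0.217 + 0.118 = 0.335.

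| SGB v control risk | Fisher power | Boschloo power |
|---|---|---|
| 40% v 10% | 9.5% | 19.5% |
| 50% v 10% | 21.7% | 33.5% |
| 60% v 10% | 39.3% | 49.3% |

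Fisher's test reaches 80% power only at about 80% v 10%.

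**True size** (both arms at the same risk):

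| Common risk | Fisher | Boschloo |
|---|---|---|
| 10% | 0.04% | 0.43% |
| 20% | 0.44% | 1.98% |
| 30% | 1.19% | 2.77% |
| 50% | 2.13% | 2.55% |
| maximum | 2.1% | 2.8% |

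**What an interval would show.** With 0/8 events the exact two-sided 95% upper limit is 1 − 0.025^(1/8) = 36.9%. With 4/8 the exact interval is 15.7% to 84.3%. For 4/8 v 0/8 the difference is 50 points, with a Newcombe 95% interval of about 7 to 78 points. That interval is shown for illustration and is not an exact one.

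**The case against.** The strongest reply is that safety does not rest on this test. Description leads the safety analysis, so a 4 v 0 split would be visible by arm whatever the p value. The DSMB reviews weekly or on each potential SAE, may ask for analyses by treatment group (Section 13.0), and has a stopping guideline. Suppose that guideline is applied to all 16 patients pooled, with alternating allocation and at most one event per patient (assumptions). It then triggers with probability about 83% at 50% (SGB) v 10% (control). This stands as separate protection, but it does not compare arms: with the risks reversed, it still triggers with probability about 76%.

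A reader might infer that a real excess of harm will be reported as no difference. The documents do not support that. No section says so, and the one remark on non-significant results, under Secondary measures in Section 10.0, carries trends forward to a larger trial. That remark is not made for safety, so the plan contains no explicit caution either way.

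A reader might also infer that the plan is bound to a test that cannot declare 4/8 v 0/8 significant. Fisher's test is only an example, and the result depends on an unstated two-sided 5% level; one-sided, the table is significant and power at 50% v 10% is 33.5%. Nor is the true error rate always below 1%: it passes 1% at a common risk of about 28% and peaks at 2.1%. Low size is not itself a harm; low power is the weakness.

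Finally, Boschloo's test changes few verdicts: 3 v 0, 5 v 1, 6 v 2 and 7 v 3 remain non-significant under both. The limit is the sample size, so the change of test is a secondary gain. On counting, the reference to percentage of occurrence suggests patients, but the text does not settle it.

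**Conclusion.** The concern holds as a gap in reporting and specification, not as an error that invalidates the safety analysis. Fisher's test is valid here. At 8 v 8, with an assumed two-sided 5% level and a 10% control risk, it misses a true 50% v 10% excess about 78% of the time (100 − 21.7). Its non-significance alone therefore carries little information about harm, and the plan supplies no interval that would show this. Boschloo's test cuts the miss rate to about 66% (100 − 33.5) with size still at most 2.8%, so power remains low. This is an improvement available at almost no cost, and most of its value lies in the interval.

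**What to change.** In the safety paragraph of Section 10.0, and by reference in Section 6.0(d):

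1. Define the compared quantity as the number of patients with at least one event, per arm and per event category.
2. Report the risk difference with an exact unconditional 95% confidence interval, and the SGB-arm rate with its exact 95% interval, whatever the p value.
3. State alpha and sidedness for the adverse-event comparison.
4. Name Boschloo's test in place of Fisher's, as an exact test that is never less powerful.
5. State that a non-significant result is not evidence of equal safety.

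The cost is a few lines of text and standard software. Design, enrolment, data collection and the stopping guideline are unchanged.

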Available research indicates that an exaggerated immune response plays a key role in the cardiopulmonary pathophysiology of COVID-19. Preliminary data from previous studies at UNMC suggest that acute lung injury initiates robust and sustained macrophage activation in thoracic dorsal root ganglia and in stellate ganglia, resulting in increased cardiac and pulmonary afferent and efferent neuronal sensitivity. In the current proposal, we plan to validate a novel therapeutic strategy to treat coronavirus-induced cardiopulmonary symptoms and complications by local delivery of bupivacaine, dexamethasone, and clonidine to the stellate ganglia. Single injection and continuous infusion SGB have been safely utilized clinically and in many human studies.

Section 3.0 Eligibility Criteria:

Inclusion:

- Subject admitted to COVID ICU/progressive care, age 40-75 years old

Subjects must have + covid test with signs of impending respiratory compromise as identified by having at least 2 of the following:

- Respiratory rate ≥ 30 breaths per min
- Oxygen saturation at rest $\leq 93\%$
- $\text{PaO}_2/\text{FIO}_2 \leq 200$ mm Hg
- bilateral infiltrates on chest radiograph or CT not due to cardiac failure
- Requiring non-invasive or invasive mechanical ventilation.

Any patient with a + covid test and any cardiac tachydysrhythmia (excluding sinus tachycardia) will be included regardless of respiratory status. (Note: The broader inclusion of patients who have cardiac tachydysrhythmia is based on our prior experience and other reported beneficial antiarrhythmic effects of SGB in this patient group.)

Exclusion:

- Hemodynamic instability (>2 vasopressors)
- Heart rate < 60 beats per minute
- Systolic Blood pressure of less than 80 mmHg
- pre-hospital diagnosis of heart failure or fluid overload
- anatomical inability to perform block
- prior sympathectomy
- Patient currently enrolled in another clinical trial for COVID-19 or respiratory distress/ARDS
- Uncorrectable coagulopathy
- ECMO already engaged
- On Nitric Oxide
- Pre-existing multi-organ failure (>2 organ systems)
- Allergic to dexamethasone, clonidine, or bupivacaine.
- If female, currently pregnant or breast-feeding.
- Investigators determine the subject would be too unstable to participate in the study intervention.

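### Arrhythmia and ventilation are compared by time-to-event methods and by duration of use, but some patients enter already in those states, and no at-risk set or rule for death is given

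*Combined protocol and SAP*

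**What the plan says.** **Endpoints and analysis.** The secondary measures in Section 10.0 list occurrence of cardiac arrhythmias, "need for mechanical ventilation and/or ECMO as well as overall survival will be compared using time-to-event based methods (e.g. Kaplan-meier curves"). Section 6.0 gives the matching comparisons: item (e) is "frequency and time to occurrence of cardiac arrhythmias", and item (f) is the frequency of "need for and duration of use mechanical ventilation and/or extracorporeal membrane oxygenation (ECMO"). Survival is a separate item (g), followed to 90 days. Section 10.0 names no analysis for duration.

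**Entry.** Section 3.0 requires any two of five respiratory criteria, one of which is "Requiring non-invasive or invasive mechanical ventilation". A second route is open: "Any patient with a + covid test and any cardiac tachydysrhythmia (excluding sinus tachycardia) will be included regardless of respiratory status". The attached note explains that these patients are wanted because an antiarrhythmic benefit is expected. ECMO is treated differently, since "ECMO already engaged" is an exclusion.

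**Data.** The Section 7.0 baseline list includes "Current type of ventilation and oxygen use" and "Need for mechanical ventilation or other support". It has heart rate but no rhythm entry. Section 5.0 lists heart rhythm and new dysrhythmias among items taken from the medical record. The Brief Summary runs data collection through Day 5, followed by discharge information and a 90-day call. The schedule of events also marks data collection at discharge.

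**Related text.** Under the primary objective, Section 10.0 also plans Kaplan-Meier methods for time to thresholds, which it does not list.

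**The concern.** A time-to-event comparison needs a defined event, a set of patients who can still have it at time zero, and a rule for patients who die first. None of the three is stated for arrhythmia or ventilation. For ECMO the entry exclusion settles the at-risk set, but the rule for death is still missing.

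Entry criteria and endpoints overlap. Section 3.0 uses mechanical ventilation for both non-invasive and invasive support, and the endpoint does not say which counts. The tachydysrhythmia route recruits patients in the very state whose time to occurrence is to be compared.

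Death matters in two ways. If deaths are censored and one minus Kaplan-Meier (1-KM) is read as incidence, the figure is too high. If duration of use is compared with no allowance for death, an arm with more early deaths can look better. Section 10.0 says that non-significant trends in these outcomes will be taken up in a larger trial, so their meaning and direction are what this trial hands on.

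**Working it through.** The plan states no rate, event count or power for arrhythmia, ventilation or death, so there is no figure of its own to reproduce. From the documents: 16 patients, 8 per arm (Section 5.0), so one patient is 100/8 = 12.5 percentage points. **Every rate and duration below is an assumption.**

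**1. Who can have a first event**

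| State at entry | Possible under Section 3.0? | First onset still possible? |
|---|---|---|
| Invasive ventilation | Yes | No |
| Non-invasive ventilation | Yes | Yes for invasive ventilation; no if the two types are pooled |
| Ongoing tachydysrhythmia | Yes | Not of that arrhythmia; yes of another type |
| ECMO | No, excluded | Yes |

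**2. Reading 1-KM as incidence when deaths are censored**

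Take constant hazards over one unit of follow-up, true incidence 0.30 and a proportion d dying first. The total hazard is H = -ln(0.7 - d), the event hazard is h = H × 0.3/(0.3 + d), and 1-KM = 1 - exp(-h).

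| d | H | h | 1-KM |
|---|---|---|---|
| 0.10 | 0.511 | 0.383 | 31.8% |
| 0.30 | 0.916 | 0.458 | 36.8% |
| 0.40 | 1.204 | 0.516 | 40.3% |

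The excess over 30% is 1.8, 6.8 and 10.3 points: negligible at 10% deaths, material at 30% to 40%.

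**3. Cumulative incidence also moves with deaths**

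Hold the event hazard at 0.383.

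- Death hazard 0.128: incidence = 0.383/0.511 × (1 - exp(-0.511)) = 30.0%, with 10% dying first.
- Death hazard 0.688: incidence = 0.383/1.071 × (1 - exp(-1.071)) = 23.5%, with 42% dying first.

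Cumulative incidence is therefore a correct description, but it can be read only beside deaths by arm.

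**4. Duration of ventilation**

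Let all 8 patients in an arm be ventilated for 10 days. In the comparison arm, 2 of the 8 die at day 2.

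- Mean duration: 10.0 days against (6 × 10 + 2 × 2)/8 = 8.0 days. The arm with deaths looks better.
- Days alive and free of ventilation over 28 days (example window, death scored zero): 18.0 against (6 × 18 + 2 × 0)/8 = 13.5. The direction is now right.
- The same measure cut at Day 5: zero for every patient, so it cannot separate death from continued ventilation.
- Ranking with death worst and survivors tied: the arm with deaths has a win probability of (6/8) × 0.5 = 0.375, against 0.50 for no difference.

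**5. What restricting to patients at risk leaves**

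With baseline prevalence p, the number at risk per arm is binomial(8, 1 - p). The chance that at least one arm has 2 or fewer is 1 - (1 - P(≤2))².

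| p | Expected per arm | P(≤2) in one arm | At least one arm ≤2 |
|---|---|---|---|
| 25% | 6 | 0.004 | 1% |
| 50% | 4 | 0.145 | 27% |
| 75% | 2 | 0.679 | 90% |

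**The case against.** The best defence is that these are secondary outcomes, marked in Section 1.0 for confirmation at a later phase, in a trial where any estimator is descriptive. Survival by arm is already planned, so an excess of deaths would be visible. Baseline ventilation is listed, rhythm must be known for anyone admitted by the tachydysrhythmia route, and the reference to new dysrhythmias points to incident events. All of this limits the consequence. None of it is an analysis rule, and a separate survival curve does not correct a duration that death has shortened.

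Several stronger readings are tempting, and the documents do not support them:

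- **Patients who enter in these states can have no event.** Someone on non-invasive support may progress to invasive ventilation, and someone with one arrhythmia may develop another.
- **The plan censors deaths in a Kaplan-Meier analysis.** Kaplan-Meier is only an example and censoring at death is not stated. Censoring deaths is also a legitimate basis for comparing cause-specific hazards. The overstatement arises only if 1-KM is then read as incidence.
- **A comparison of unadjusted mean duration is planned.** Section 6.0 (f) names duration of use, and no method is given. The fault is an unspecified analysis.
- **Patients already in the state will be counted as events at time zero.** No section says so.
- **The primary analysis is untouched.** The Kaplan-Meier analysis of time to thresholds under the primary objective has the same gap.

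**Conclusion.** The point holds as a gap in specification. Entry criteria overlap with the arrhythmia and ventilation endpoints, and neither an at-risk set nor a rule for death is stated. The rule for death is also missing for ECMO, and both are missing for the primary-objective threshold analysis. Overall survival by Kaplan-Meier is sound as planned.

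The size cannot be fixed from the documents. On the assumed rates, the incidence error runs from under 2 points with 10% deaths to about 10 points with 40%, and two early deaths in eight can shift mean duration by 2 days in the favourable direction. The results will be descriptive whatever method is used, so this concerns meaning and direction, not power. It is worth correcting because it is cheap and because these trends are to inform a later trial.

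**What to change.** 1. State whether the ventilation endpoint is invasive only or either type. Analyse new ventilation among patients not on that type at randomisation. Define new-onset arrhythmia as a type not present at baseline, and add a rhythm entry to the Section 7.0 baseline list. Report patients already in each state by arm and, for arrhythmia, its resolution or recurrence.
2. Use cumulative incidence (Aalen-Johansen) with death as a competing event, shown beside deaths by arm. Keep Kaplan-Meier for overall survival. Give the threshold analysis under the primary objective its own at-risk and death rule.
3. For all patients, replace duration of use with days alive and free of ventilation (death scored zero) or a ranking with death worst. Use one pre-set window longer than Day 5. Take dates from the medical record to discharge, and state a rule for patients discharged before the window ends, including any still ventilated. The Day 90 list asks about oxygen use, not ventilation dates.
4. Section 9.0 withdraws patients for arrhythmia during the initial procedure. With no sham procedure, this can happen only in the block arm. Keep these patients in the analysis and count the event.
5. Label the results descriptive.

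**Cost.** SAP wording, minor programming, one baseline entry and abstraction of ventilation start and stop dates. The main downside is a smaller at-risk set: about 6, 4 or 2 patients per arm at an assumed 25%, 50% or 75% baseline prevalence. For arrhythmia, patients leave the at-risk set only for the type they already have. The measure in step 3 keeps all 16.
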